**b. Phase 2 Trial:** A multicenter, phase II, randomized, double-blind, stratified study enrolled individuals ≥65 years of age to receive either 15 µg versus 60 µg of TIV. Oral temperature, injection site, and systemic symptoms and signs were recorded in a diary daily for one week after immunization. Sera were obtained before immunization and one month after immunization. A total of 414 subjects were enrolled, 206 received HD-TIV and 208 received standard dose TIV (SD-TIV). Subjects given the HD-TIV reported more local and systemic reactions but only local pain and myalgia were significantly increased. The HD-TIV vaccine induced a higher frequency of serum antibody increases (≥4-fold) in both HAI (16.8-27.9%) and neutralization tests (11.9-24.5%) for all three vaccine viruses in the total group as well as in subjects vaccinated and not vaccinated the previous year. Mean titers of antibody attained, the magnitude of antibody increases, and the frequencies of persons with final HAI antibody titers ≥1:32, ≥1:64, and ≥1:128 were all greater for the HD-TIV group in both serologic tests (e.g., HAI and neutralization assays), for all titer groups ≥1:32, ≥1:64, and ≥1:128), and for all vaccine viral strains compared to the SD-TIV.

**c. Phase 3 and 3b Trials, HD-TIV has Increased Immunogenicity and Efficacy in the Elderly:** A phase III, multicenter, randomized, double-blind study enrolled individuals ≥65 years of age to compare HD-TIV to SD-TIV. HD-TIV was administered to 2575 subjects and SD-TIV was administered to 1262 subjects. Individuals who received HD-TIV had higher mean post-vaccination GMT (**Table 1**). The HD-TIV vaccine met superiority criteria for both influenza A

Table 1.	HD-TIV	SD-TIV	GMT ratio
H1N1	116	67	1.7
H3N2	609	333	1.8
B	69	52	1.3

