**Influenza Surveillance:** Active surveillance for influenza-like symptoms will begin when influenza season starts at each site's community. Influenza season begins in the specific community, defined as in previous trials by identification of at least 2 positive respiratory tests for influenza, with at least 10% of diagnostic tests positive during 2 consecutive weeks in the local clinical or research laboratory. During the influenza season, the participants will be carefully followed for influenza like illness (ILI) with weekly telephone and/or electronic communications by the study staff.

If subjects meet ILI criteria (see below), a nasal swab will be collected and PCR testing for influenza and other respiratory viruses will be performed at VUMC.

If they have any of the following:

1. **Fever:**  $\geq 38.3^{\circ}\text{C}$  ( $101^{\circ}\text{F}$ ); or
2. **Two or more of any of the following:** respiratory symptoms (rhinorrhea, sinus congestion, post-nasal drip, shortness of breath, cough, wheezing, sputum production, sore throat, sneezing, watery eyes, ear pain, hoarseness) or systemic symptoms (myalgias and headache).

Additionally, we will attempt to collect nasal swabs from subjects who meet the ILI criteria during the study time (out of the flu season). Nasal swabs will be obtained at all scheduled visits to document the occurrence of influenza virus detection both prior to and after vaccination.

Data regarding about any breakthrough clinical influenza illness will be collected during the study period and until June 30th.

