### b. Secondary Objectives:

- i. To determine whether HD-TIV compared with SD-QIV will increase the probability of achieving a  $\geq 4$ -fold rise in HAI titers,  $\geq 1:40$  HAI titer, or higher GMT titers to influenza B antigens in adult HSCT recipients.
- ii. To determine the frequency and severity of solicited local injection site adverse events (e.g. pain/ tenderness, redness, and swelling/induration at injection site) with HD-TIV compared to SD-QIV in adult HSCT recipients.
- iii. To determine the frequency and severity of solicited systemic adverse events (e.g. fevers, headache, fatigue/malaise, nausea, body ache/myalgia, general activity level, and vomiting) with HD-TIV compared to SD-QIV in adult HSCT recipients.
- iv. To define the relationship between HAI titers, *in vivo* T and B cell phenotype, and *in vitro* influenza-specific T and B cell response in adult HSCT recipients receiving either HD-TIV or SD-QIV.
- v. To correlate HAI responses to MN responses.
- vi. To compare the persistent HAI and MN titers for all four antigen seven months after the last vaccine dose to assess for persistence of antibody titers.
- vii. To compare influenza detection by PCR during influenza season in adult HSCT recipients receiving either HD-TIV or SD-QIV.
- viii. To assess HAI and MN response in patients (e.g. repeaters) undergoing two-consecutive years revaccination using the same antigen dose
- ix. To correlate HAI responses to neuraminidase inhibition titers (NAI).

**3. Study Area:** The study will be conducted in the Oncology Units or Clinics, or Clinical Trial Centers at the following sites: **Table 2** includes the yearly average number of transplants per site.

Table 2. Clinical Sites	Average Number of Yearly Allogeneic Transplants
Northwestern University Feinberg School of Medicine	167
Fred Hutchinson Cancer Research Center	300
University Hospital, University of Alabama at Birmingham	90
Vanderbilt University Medical Center	108
TOTAL	665

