## 7. Reporting Adverse Events:

The investigator is responsible for reporting:

- Any Grade 3 Adverse event that is not attributable to underlying disease for which the transplant was undertaken, **or** not attributable to GVHD, **or** not attributable to complications of immunosuppressive medications that are observed or reported through 7 days following vaccination (Day 0 through Day 7), regardless of their relationship to study product.
- Any other AE will not be reported unless it meets the SAE criteria (see Section 16.f).

Initial vaccine reactions will be assessed for at least 15 minutes after each vaccination. Subjects will be asked to record both solicited vaccine reactions and any unsolicited AEs on a memory aid for 7+ days after each vaccination (Day 0 through Day 7). Study personnel will attempt to contact the subjects by telephone and/or electronic communication at 1-3 days and 8-10 days after vaccination to review any AEs and SAEs. Adverse events and SAEs will be collected through 7 days following vaccination.

**Solicited systemic AEs** will be collected for 7+ days post each vaccination and will include the following: fevers, headache, fatigue/malaise, nausea, body ache/myalgia, general activity level, and vomiting. **Solicited injection site AEs** will include the following: pain, tenderness, redness/erythema, and swelling/induration at injection site.

**Reporting of Deviations:** All deviations will be reported to the Institutional Review Board (IRB) at the time of annual continuing review. Note: if the deviation affects patient safety and/or risk, the event will be reported immediately.

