#### **Visit 1: Day 0:**

- Subject will sign written Informed Consent if not already signed prior to Visit 1.
- Brief review of Medical history
  - Inclusion/exclusion criteria will be checked.
  - Prior/concomitant medications will be recorded.
  - Written documentation of prior influenza immunizations post-transplant will be collected.
- Targeted physical examination will be conducted including measurement of oral temperature (must be  $\leq 100.4^{\circ}\text{F}/38^{\circ}\text{C}$ ). Except for oral temperature, if a physical exam is completed as a part of standard of care, another physical exam does not need to be completed.
- For females of childbearing potential a pregnancy test will be performed.

- Approximately 30-60 mL of blood will be collected by venipuncture or from a central line prior to vaccination for HAI and MN assays to influenza virus antigens, phenotypic B, and T cell responses, B and T cell specific influenza responses, CBC d/p, quantitative CD4+/CD8+/CD19+ levels, and quantitative serum IgG and IgM concentrations (if CBC d/p, quantitative CD4+, CD8+, CD19+, IgM, and IgG are obtained as part of standard of care prior to enrollment and on the same calendar day as vaccination, these data will be collected and will not need to be repeated).
- Study vaccine will be administered.
- Study staff will observe the subjects closely for at least 15 minutes post-vaccination, with appropriate medical treatment readily available in case of rare anaphylactic reaction following the administration of vaccines.
- If IVIG/SCIG is given the same day, it must be given after the vaccination, and a second blood draw will be obtained post-IVIG/SCIG if administered on same calendar day.
- A memory aid form with reaction measurements, a measurement gauge, thermometer and instructions will be provided for the subject to record oral temperatures and any general or local reactions occurring during the vaccination day (day 0) and the next 7 days. Information on the memory aid form will be collected from the subject through telephone calls and/or electronic communication in the week following vaccination or received by mail. . If memory aid data were not received by any of the methods mentioned, subjects may return it on the day of their next visit.

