groups will be estimated by calculating the posterior 95% credible interval of the difference in proportions. For continuous-valued events (e.g. size of swelling) uninformative priors will be used as described in (17.b); for discrete events, a flat beta parameter with scale=shape=1 will be used as uninformative priors. For each group and each event, solicited and unsolicited AEs will be descriptively summarized. Severities of solicited and unsolicited AEs will also be descriptively summarized for each group and each type of event. Descriptive statistics will include number experiencing event, mean and 95% posterior credible interval. Maximum size of redness and swelling may be descriptively summarized for each group and event; proportion of events lasting longer beyond Day 3 may also be descriptively summarized. Subjects with missing data will be excluded from analysis, but the sensitivity of the results to missingness will be formally analyzed by comparing posterior estimates under the range of possible outcomes for the missing individuals.

- d. Influenza-Like-Illness assessment:** The percentage of individuals in each group that test positive for influenza by PCR and the number of ILIs in each group during the influenza season will be compared.

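### The in-season ILI count has no rule separating Day 0-7 vaccine reactions from illness, so reactions to doses given in season can be counted as ILI

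*Combined protocol and SAP*

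**What the plan says.** - **ILI definition** (Section C.1, Influenza Surveillance; repeated in substance under the ILI Visit in C.14). Fever of 38.3 °C or more qualifies alone. Otherwise the criterion is "Two or more of any of the following", a list of respiratory symptoms "or systemic symptoms (myalgias and headache"). No respiratory symptom is required.
- **Solicited systemic reactions** (C.7). These are "fevers, headache, fatigue/malaise, nausea, body ache/myalgia, general activity level, and vomiting". The memory aid covers "general or local reactions occurring during the vaccination day (day 0) and the next 7 days" (C.14, Visit 1, repeated at Visit 2). In Table 5, 38.3 °C is the lower bound of Grade 2 fever, which is also the ILI fever threshold.
- **When ILIs count.** C.1 states: "Active surveillance for influenza-like symptoms will begin when influenza season starts at each site's community". Season onset depends on local test positivity.
- **Analysis** (C.17.d). Alongside the percentage PCR-positive, "the number of ILIs in each group during the influenza season will be compared". No model, post-dose window or attribution rule is given.
- **Objective** (C.2.b, secondary objective vii). "To compare influenza detection by PCR during influenza season in adult HSCT recipients". The ILI count itself is not a listed objective.

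**The concern.** The same symptoms on the same days can be a solicited adverse event and an ILI, and no section says which category takes precedence. A subject vaccinated after local season onset who has headache and myalgia the next day meets both definitions.

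The trial's only comparison of symptomatic illness would then mix illness with reactogenicity. If reactions are equally common in the two arms, the added events pull any real ILI difference towards a ratio of 1. If they are not, the count moves against the arm with more systemic reactions, whichever that is.

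**Working it through.** **Step 1. Can a reaction alone meet the ILI definition?** Yes, by two routes: headache plus myalgia, or fever of 38.3 °C or more. All three symptoms are on the C.7 solicited list. C.11.b describes systemic reactions that start 6 to 12 hours after vaccination and can last 1-2 days.

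**Step 2. Can the Day 0-7 window fall in season?** Yes.
- There is no calendar cut-off for enrolment or dosing.
- Eligibility starts 3 months after transplant, which patients reach at any time of year.
- Dose 2 follows dose 1 by 28-42 days, so local onset can fall between them.
- Exclusion criterion 6 (C.4.b) removes people with proven influenza after September 1 and before enrolment, so enrolment while influenza circulates is anticipated.
- Table 3 places the influenza season column after Visit 3, but that is layout, not a restriction.

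Doses given before local onset do not contribute.

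**Step 3. Which direction do the documents support?**

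| Source | HD compared with SD |
|---|---|
| B.3.b, phase 2, age 65 and over | Of the reactions, "only local pain and myalgia were significantly increased" with HD |
| B.4.b, paediatric solid organ transplant | More fatigue and body ache with HD |
| B.4.a, adult HSCT (closest population) | No systemic difference |
| B.4.f, adult kidney/liver transplant | No systemic or local difference |
| B.4.c, paediatric leukaemia | More fatigue and headache with SD |
| Hypothesis 2 (Section A) | Similar safety profile expected |

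No section reports more fever or more headache with HD. The direction is unsettled.

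**Step 4. Possible size.** The plan gives no figure for the ILI comparison, so there is none to reproduce. Its 69 per arm (C.5, C.17.a) is the only documented input. Everything else below is assumed:
- *s*, the share of subjects with one in-season dose: 0 to 100%
- *r*, the probability that a reaction to that dose meets the ILI criteria: 10% or 20%
- true ILIs per arm: 10 or 20

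Reaction-only ILIs per arm = 69 × *s* × *r*. Ratio = (true + reaction-only, HD) / (true + reaction-only, SD).

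At *s* = 50%, 69 × 0.5 × 0.20 = 6.9 and 69 × 0.5 × 0.10 = 3.45. With 20 true ILIs per arm:
- 20% HD v 10% SD: 26.9 / 23.45 = 1.15
- equal rates: 1.00
- 10% HD v 20% SD: 23.45 / 26.9 = 0.87

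Full range, where the true ratio is 1.0:

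| *s* | True ILIs per arm | 20% HD v 10% SD | Equal rates | 10% HD v 20% SD |
|---|---|---|---|---|
| 0 | 10 or 20 | 1.00 | 1.00 | 1.00 |
| 25% | 20 | 1.08 | 1.00 | 0.93 |
| 50% | 20 | 1.15 | 1.00 | 0.87 |
| 100% | 20 | 1.26 | 1.00 | 0.80 |
| 25% | 10 | 1.15 | 1.00 | 0.87 |
| 50% | 10 | 1.26 | 1.00 | 0.80 |
| 100% | 10 | 1.41 | 1.00 | 0.71 |

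**Step 5. Dilution with equal rates.** Suppose the true counts are 10 HD v 20 SD, a ratio of 0.50, and *s* = 50%. At *r* = 10% in both arms, 13.45 / 23.45 = 0.57. At *r* = 20% in both arms, 16.9 / 26.9 = 0.63.

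**Step 6. With a Day 0-7 counting rule.** Reaction-only episodes with no respiratory symptom and no positive swab leave the count. The ratios return to 1.00 in Step 4 and 0.50 in Step 5.

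**The case against.** The case against makes five points.

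1. **Direction.** A reader might infer that the comparison is tilted against HD-TIV, because myalgia was commoner with the high dose in the elderly phase 2 trial. The documents do not support that. The adult HSCT trial found no systemic difference and paediatric leukaemia patients had more headache with SD. The headache-plus-myalgia route needs both symptoms, and no section shows HD raising headache or fever. C.11.b adds that in placebo-controlled trials split-virus vaccine did not raise systemic symptoms in older or healthy young adults. This objection stands against any claim about sign. It does not remove the missing rule.
2. **Season.** Only in-season doses matter, and their share is not given. It could be near zero, in which case the problem disappears. This stands as a limit on size.
3. **PCR.** A reader might also infer that false ILIs contaminate objective vii. A reaction cannot turn a swab influenza-positive. Swabs are already taken regardless of symptoms at Visits 1 to 4 and at the optional visits. What remains is a few additional ILI-triggered swabs, a small change in detection opportunity whose balance between arms is unknown.
4. **Importance.** The ILI count is not a listed objective and has no powering or decision rule. This stands, and it keeps the point modest.
5. **Sensitivity.** A broad definition is reasonable for triggering swabs in immunosuppressed patients. Agreed, but a good swab trigger need not also be the counting rule for an endpoint.

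**Conclusion.** The gap is clear from the text. Two routes into the ILI definition consist only of solicited vaccine reactions, in-season doses are not prevented, and C.17.d counts every in-season ILI. Followed as written, the plan would count some reactions as illness whenever doses are given after local season onset.

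The size and sign of the effect cannot be derived from the documents. Under the assumed inputs, a true ratio of 1.0 could appear as anything from 0.71 to 1.41. It stays at 1.00 if reaction rates are equal or no dose falls in season. Equal rates would still move a true ratio of 0.50 to between 0.57 and 0.63 with half of subjects dosed in season. These figures ignore dropout and assume one in-season dose per subject, with each reaction counted as a separate ILI. Two in-season doses per subject would double the reaction-only counts.

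A directional bias against HD-TIV is possible but not established, and the PCR comparison is not inflated by reactions. This is an inexpensive improvement to a supporting comparison.

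**What to change.** In C.17.d, add that an episode with onset on Day 0-7 after a study vaccination is not counted as an ILI unless it includes at least one listed respiratory symptom or its swab is influenza-positive. Report the unrestricted count as a sensitivity analysis, so that the effect of the rule is visible. Settle this before unblinding.

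Leave the ILI criteria unchanged as the swab trigger, and keep every influenza-positive PCR result in the objective vii comparison. A Day 0-7 exclusion on PCR results could discard true detections. Optionally, report scheduled and ILI-triggered swabs separately by arm.

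The cost is a sentence or two in the analysis section and a recorded onset date for each ILI. C.14 times specimen collection from symptom onset, so sites need that date already, but the documents do not list it as a collected field. A few true non-influenza illnesses without respiratory symptoms in the first week after a dose will not be counted. The rule also leaves in an episode that combines one reaction symptom with an incidental respiratory symptom.

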## 2. Primary and Secondary Study Objectives:

### a. Primary Objectives:

- i. To determine whether HD-TIV compared with SD-QIV will increase the probability of achieving a  $\geq 4$ -fold rise in HAI titers,  $\geq 1:40$  HAI titer, or higher GMT titers to influenza A antigens in adult HSCT recipients.

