## A. Specific Aims and Hypothesis:

1. **Hypothesis 1:** *We hypothesize that the high dose trivalent inactivated influenza vaccine (HD-TIV) group will have a greater frequency of  $\geq 4$ -fold rise and HAI titer  $\geq 1:40$  and higher geometric mean titer (GMT) to influenza A antigens compared to the standard dose quadrivalent inactivated influenza vaccine (SD-QIV) group.*

**Specific Aim #1:** To determine whether HD-TIV compared with SD-QIV will increase the probability of achieving either a  $\geq 4$ -fold rise in HAI titer, a HAI titer  $\geq 1:40$ , or a higher GMT to influenza A antigens in adult HSCT recipients.

2. **Hypothesis 2:** *We hypothesize that HD-TIV will be well tolerated, with a safety profile similar to SD-QIV.*

**Specific Aim #2:** To determine the frequency and severity of solicited local injection site adverse events and solicited systemic adverse events related to HD-TIV compared with SD-QIV in adult HSCT recipients.

3. **Hypothesis 3:** *We hypothesize that HD-TIV vaccination will induce higher protective HAI titers and higher frequencies of circulating activated T-follicular (Tfh) cells and circulating B cell plasmablasts, it will also induce higher levels of influenza-specific B and T cell responses compared to SD-QIV.*

**Specific Aim #3:** To define the relationship between HAI titers, *in vivo* T and B cell phenotype, and *in vitro* influenza-specific T and B cell responses in adult HSCT recipients receiving either HD-TIV or SD-QIV.

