## 10. Investigational Product and Risk Information:

Fluzone Quadrivalent® is a Federal Drug Administration (FDA)-approved vaccine and is recommended for all patients ≥6 months.

Fluzone® HD-TIV has not yet been approved for individuals <65 years of age. The current seasonal influenza vaccine will be used throughout the entire study.

- a. **Acquisition:** Fluzone Quadrivalent® and Fluzone® HD, preservative free, licensed product formulated for the 2017-2018, 2018/2019, and/or 2019/2020 influenza season will be donated by Sanofi Pasteur and distributed to each site of the 4 institutions.
- b. **Formulation, Packaging, and Labeling:** Fluzone Quadrivalent® and Fluzone® HD, preservative free, licensed product, Sanofi Pasteur, Swiftwater, PA. The 2017-2018 influenza strain recommendations are the following: A/Michigan/45/2015 (H1N1)-like virus; an A/Hong Kong/4801/2014 (H3N2)-like virus; and a B/Brisbane/60/2008-like virus (this is a B/Victoria lineage virus) for both HD-TIV and SD-QIV; and in Fluzone Quadrivalent®, additional B virus, B/Phuket/3073/2013-like virus (this is a B/Yamagata lineage virus). The Fluzone package inserts for the 2017-2018 influenza season for both vaccines will be available in the Protocol Library.
- c. Fluzone Quadrivalent® and Fluzone® HD, preservative free, licensed product formulated for the 2018-2019 influenza season, Sanofi Pasteur, Swiftwater, PA will be obtained. Formulation, Packaging, and Labeling: Fluzone Quadrivalent® and Fluzone® HD, preservative free, licensed product, Sanofi Pasteur, Swiftwater, PA. The 2018-2019 recommendations are the following: A/Michigan/45/2015 (H1N1)pdm09-like virus; an A/Singapore/INFIMH-16-0019/2016 (H3N2)-like virus; and a B/Colorado/06/2017-like virus (this is a B/ Victoria lineage virus); and in Fluzone Quadrivalent®, additional B virus, B/Phuket/3073/2013-like virus, (this is a B/ Yamagata lineage virus). The Fluzone package inserts for the 2018-2019 influenza season for both vaccines will be available in the Protocol Library.

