**17. Statistical Considerations:**

- a. Sample Size Calculations:** A target of 138 subjects will be targeted, with 69 in each group. This is based on the assumption, with 80% power, that 25-30% of the subjects in the SD group will achieve a protective titer compared to 50-60% of the HD-TIV group for at least one influenza antigen. Accounting for a 20% drop out rate, 138 subjects will be recruited.

Strain	Expected Seroprotection HD-TIV	Expected Seroprotection SD-QIV	N (HD)	N (SD)	Power	Total N with 20% drop out
Expected HD-TIV seroprotection is twice as of SD-QIV						
A	40%	20%	80	80	80%	200
A	50%	25%	55	55	80%	138
A	60%	30%	40	40	80%	100
A	70%	35%	28	28	80%	70

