- b. Immunogenicity analysis:** The probability of achieving a 4-fold (or greater) rise in post-vaccination HAI titers relative to baseline, as well as the probability of a HAI titer greater than 1:40, will be estimated using a binomial model, using the full analysis set. We will calculate the Bayesian posterior distribution of the probabilities under all 4 combinations of SD- and HD-TIV crossed with a single dose and two doses. From these probabilities, odds ratios will be calculated along with 95% credible intervals. These quantities will be modeled as a logit-linear function of several covariates, including CD4+/CD8+/CD19+, and IgG/IgM levels, absolute neutrophil and lymphocyte count (or their ratio), time from post-transplant to enrollment, type of preparative regimen, donor status, and stem cell source. We will use normal priors with standard deviation of 5 for all logit-linear coefficients and the baseline mean, which are not informative when transformed to the probability scale. Scale (standard deviation) parameters will be given long-tailed half-Cauchy priors, also in the interest of being uninformative. In addition, the distributions of geometric mean HAI titers for high and SD-QIV recipients will be estimated via log-normal models, and expressed as ratios in order to evaluate the evidence for higher GMT in the HD-TIV sample, after one and two vaccines. The scale parameters for priors under the log-normal model will be increased by an order of magnitude relative to the logit-linear models to ensure that they do not influence the posterior estimates. We will compare each group to document if they meet serological criteria by WHO biological standards for influenza vaccines (>40% for seroconversion, GMT >2.5-fold increase, and >70% with ≥1:40). Subjects with missing data will be excluded from the analysis, but the sensitivity of the results to missingness will be formally analyzed by comparing posterior estimates under the range of possible outcomes for the missing individuals.
- c. Safety analysis:** For the primary analysis of the safety data, the proportion of subjects in each group (using full analysis set) experiencing at least one solicited AE will be calculated along with 95% posterior credible intervals. The difference between the rates of solicited AEs between the

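### Hypothesis 1, the primary objective and the sample size imply different success rules, and no visit, strain rule, threshold or multiplicity control says which of up to 12 contrasts decides the trial

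*Combined protocol and SAP*

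**What the plan says.** Four places bear on what would count as success.

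- **Section A, Hypothesis 1** expects more 4-fold rises, more titres of at least 1:40, "and higher geometric mean titer (GMT) to influenza A antigens compared to the standard dose" vaccine. The connective is *and*.
- **Section A, Specific Aim 1** names the same three measures as alternatives, ending "or a higher GMT to influenza A antigens in adult HSCT recipients". **Section C.2.a**, the only primary objective, does likewise: "HAI titer, or higher GMT titers to influenza A antigens in adult HSCT recipients". The connective is *or*.
- **Section C.17.a** sizes the trial on one measure, a protective titre, expected in 25–30% of the SD group "compared to 50-60% of the HD-TIV group for at least one influenza antigen". The text is not limited to influenza A, although the table rows are labelled A.
- **Section C.17.b** estimates the 4-fold rise and 1:40 probabilities "under all 4 combinations of SD- and HD-TIV crossed with a single dose and two doses", with odds ratios and 95% credible intervals. GMT ratios are used to "evaluate the evidence for higher GMT in the HD-TIV sample, after one and two vaccines".

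Each season's vaccine carries two A strains; for 2017-18 Section C.10 gives "A/Michigan/45/2015 (H1N1)-like virus; an A/Hong Kong/4801/2014 (H3N2)-like virus". No section names a primary visit, says whether one or both A strains must succeed, sets a threshold for the comparison between arms, or mentions multiplicity.

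**The concern.** The same data can be read in opposite ways. If HD-TIV is better on GMT for H3N2 after dose 1 and on nothing else, the objective in C.2.a is met and Hypothesis 1 is not. The background rationale says a positive result could change vaccine recommendations, so the rule for a positive result should be fixed before the arms are compared. Without one, the contrast that turns out favourable can become the headline. The stated power also gives no guide to how often the *or* objective would be met, whether by a real effect or by chance.

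**Working it through.** **1. The plan's own sample size.** Inputs from C.17.a: 50% v 25%, 80% power, 20% dropout. Two-sided 5% is assumed, because no level is stated. With unpooled variance:

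n = (1.960 + 0.842)² × (0.50 × 0.50 + 0.25 × 0.75) / 0.25² = 7.849 × 0.4375 / 0.0625 = 54.94, so 55 per arm.

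110 / 0.80 = 137.5, so 138. The figure reproduces. The other rows give 79, 40 and 29 against 80, 40 and 28 stated. This is the calculation for one seroprotection contrast.

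**2. Contrasts eligible under *or*.** 3 measures × 2 A strains × 2 time points = 12. The plan never states this count; it follows from C.2.a, C.10 and C.17.b.

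**3. Chance of a false win for HD-TIV.** Assume a win is a 95% interval lying wholly on the HD-TIV side, and no true difference.

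- One contrast: 2.5%.
- Twelve independent contrasts: 1 − 0.975¹² = 26.2%.
- Twelve correlated normal statistics, with correlations between measures, strains and visits set by assumption:

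| Measures | Strains | Visits | At least one win for HD |
|---|---|---|---|
| 0.3 | 0.2 | 0.3 | 23.2% |
| 0.5 | 0.3 | 0.5 | 19.9% |
| 0.6 | 0.5 | 0.7 | 16.3% |
| 0.7 | 0.5 | 0.7 | 15.1% |
| 0.8 | 0.7 | 0.8 | 11.9% |
| 0.9 | 0.9 | 0.9 | 7.9% |

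- Simulated titres: 8,000 null trials per setting and 55 per arm, on doubling dilutions from 1:10. Assumed log2 means were 3.3, 4.2 and 4.5 (baseline, after dose 1, after dose 2), with SDs 1.5, 2.0 and 2.0. Four settings raised the between-strain correlation from 0.2 to 0.7, the correlation between post-dose visits from 0.5 to 0.9, and the correlation with baseline from 0.4 to 0.6. Results: 18.1%, 17.4%, 16.1% and 14.0%.
- Restricted to the six contrasts after dose 2, the same simulations give about 10% (independence: 1 − 0.975⁶ = 14.1%).

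**4. Power of an *and* rule.** The documents give no expected 4-fold-rise rates, GMT ratios, dose-1 responses or correlations, so this cannot be fixed. Simulations with differing assumed effects gave 55% to 80% for all three measures in one strain after dose 2, and 16% to 54% for all twelve contrasts.

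**5. Power under one explicit rule.** Take HAI of at least 1:40 after dose 2, 50% v 25%, 55 per arm, each A strain judged on a 97.5% interval. The chance of a false win for HD-TIV on either strain is then at most 2 × 1.25% = 2.5%.

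- Exact enumeration with the Pearson chi-square test: 78.9% at two-sided 5%, 69.0% at 2.5%.
- Unpooled formula: 80.0% at 5%. At 2.5%, Φ(0.25 / √(0.4375/55) − 2.241) = Φ(0.562) = 71.3%.
- At least one strain, if both have the planned effect: 69% under perfect correlation, up to 1 − (1 − 0.69)² = 90% under independence.

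**The case against.** The strongest reply is that this is a phase II trial analysed by Bayesian estimation. It adopts no test and no error rate, so the connectives merely list the measures of interest. Part of that stands: the 2.5%, the 5% level and the percentages above depend on an interval rule that the plan does not adopt. C.17.b ties 95% intervals explicitly to the odds ratios only, and states none for the four GMT contrasts. But Hypothesis 1 and C.2.a both ask whether HD-TIV is better, and a Bayesian analysis still needs a criterion for answering. The WHO criteria cited in C.17.b do not supply one, since they are applied to each arm on its own.

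Three stronger readings are tempting and are not supported.

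- *Hypothesis 1 requires all twelve contrasts.* Its *and* joins three measures and says nothing of both strains or both time points.
- *A chance win is likely.* At 12–26% it is roughly 5 to 10 times nominal, but well under one half. The larger figures obtained by counting either direction (46% under independence) include wins for SD-QIV, which do not bear on a claim for HD-TIV.
- *The trial is badly underpowered under* and. That depends on effects the documents do not give. Under some assumptions, a three-measure rule for one strain comes close to 80%.

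**Conclusion.** The concern holds as a conflict between stated success rules. Hypothesis 1, the primary objective with Specific Aim 1, and the sample size each imply a different rule, and C.17.b does not choose among them. If any of up to 12 contrasts may count, and a win is a 95% interval favouring HD-TIV, the chance of at least one false win is roughly 14–18% in the titre simulations and about 12–26% over the low-to-high correlations assumed, against 2.5% for one contrast. It falls to about 8% only if all three correlations are as high as 0.9. The 80% power describes one seroprotection contrast at an assumed two-sided 5%, so it does not describe the *or* objective. What an *and* rule would achieve cannot be settled from the documents. Confidence is high on the conflict, and moderate on the size, which rests on assumed correlations and an assumed rule.

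**What to change.** State one rule and use it in Hypothesis 1 and Specific Aim 1, C.2.a, C.17.a and C.17.b. One workable version:

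- **Primary endpoint:** HAI of at least 1:40, the only measure sized in C.17.a, at Visit 3, which follows the full two-dose regimen. C.17.a names no visit, so this is a choice to be stated.
- **Rule:** analyse H1N1 and H3N2 separately, and claim superiority for a strain only if the 97.5% credible interval of its odds ratio excludes 1 in favour of HD-TIV.
- **Supportive:** all after-dose-1, 4-fold-rise and GMT contrasts.
- **Power at 50% v 25%, 55 per arm:** about 69% per strain (79% unadjusted by exact enumeration, 80% by the plan's apparent formula), and about 69% to 90% for at least one strain, depending on between-strain correlation.

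Another single prespecified rule would serve, provided power is restated to match.

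The change is to wording only and needs no new data. It has two costs. The stated per-strain power becomes less favourable. And because new subjects were enrolled over 2017-18 and 2018-19 while this version is dated August 2019, the choice must be fixed before unblinding and documented as made without knowledge of results by arm.
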